8.3. Withdrawal Criteria

Participation in the study is strictly voluntary. Parents/guardians have the right to withdraw their children from the study at any time and for any reason. A subject's participation will be terminated:

- At their parent's/guardian's request;
- At the subject's request if ≥ 7 years old and able to give assent; in cases where a subject is < 7 years of age and expresses a wish to stop the study, the parent/caregiver and the Investigator will use their best judgments to determine what is in the best interest for the child in question;
- If, in the Investigator's or Sponsor's opinion, continuation in the study would be detrimental to the subject's well-being;
- If the subject is not able to comply with the study requirements;

- If the Sponsor terminates the study;
- If a regulatory authority requires that all study activities be halted.

In all cases, the reason for withdrawal must be recorded in the subject's medical records (source documents). If the reason for subject withdrawal is not known, the subject must be followed to establish whether the reason was an AE, and if so, this must be reported in accordance with the procedures outlined in Section 11.1.2. Vigorous attempts should be made for follow-up of all subjects who miss a study visit. In general, although study drug may be stopped, subjects will be encouraged to complete the scheduled procedures. The subject will require an Early Withdrawal Visit if withdrawn from the study prior to scheduled study completion. If a subject's participation in this study is terminated, the responsible Investigator at the site will complete a termination form.

To the extent possible, all scheduled end-of-study assessments (including the Early Withdrawal Visit) should be performed on all participating subjects who withdraw from the study before the Day 7 Visit. For subjects who withdraw between Day 7 and Day 14, a telephone assessment should be conducted, where possible.

Subjects withdrawn from the study at any time other than during the screening period will not be replaced.

9. TREATMENT OF SUBJECTS

9.1. Study Drug Dose Rationale

In Study 0816T0633 conducted by Shionogi & Co. Ltd in Japan, 117 pediatric and adolescent patients with type A or type B influenza infection who were ≥ 28 days but < 16 years of age, were treated with 1 to 5 daily doses of IV peramivir in the outpatient setting. The dose of peramivir used in that study (10 mg/kg of body weight to a maximum of 600 mg) was based on pharmacokinetic modeling and target area under the plasma concentration-time curve (AUC). Peramivir, administered IV, was generally safe and well tolerated in this population. Plasma concentrations from the pediatric patients in this study were found to be within the range of plasma concentrations following administration of peramivir at 300 mg or 600 mg in adult patients with influenza, and did not exceed mean plasma concentrations following administration at 800 mg in healthy adults.

The approved dose of peramivir in adults is a single dose of 600 mg. Population pharmacokinetic modeling performed by the FDA (July 2010) based on the Shionogi Studies 0816T0633 (children and adolescents) and 0722T0621 (adults) supports a target dose of 12 mg/kg in children (≤ 12 years) to attain exposures similar to that in adults who receive a 600 mg IV dose. Children 13 and over can be treated with 600 mg/day, the adult dose. Per CDC, the average weight of a 13-year-old boy and girl are 45 kg (99 lbs) and 46 kg (101 lbs) respectively. In adult trials of peramivir in acute uncomplicated influenza, at least 30 subjects with weights between 40 kg (88 lbs) and 50 kg (110 lbs) were treated without additional risk or complication. In addition, peramivir elimination is almost exclusively renal. Renal size reaches adult at age 12 and function (i.e., glomerular filtration rate) reaches that of an adult by age 2. The population PK model built using interim PK data from BCX1812-305 included a renal maturation factor to account for the development of renal function prior to age 2. Simulations support a dose of 8 mg/kg from birth to less than 6 months of age, and 12 mg/kg in subjects 6 months of age and older. Subjects < 6 months of age are not predicted to have higher exposure of peramivir than that of adults.

9.2. Treatments Administered

9.2.1. Peramivir

Peramivir solution for infusion is a clear, iso-osmotic, sterile, nonpyrogenic solution in 200 mg per 20 mL (10 mg/mL) single-use glass vials fitted with rubber stoppers and aluminum flip-off seals. The drug product should be stored at room temperatures up to 30°C.

Subjects < 6 months of age at time of consent will receive a single dose of IV peramivir at a dose of 8 mg/kg. Subjects ≥ 6 months $- \le 12$ years of age at time of consent will receive a single dose of IV peramivir at a dose of 12 mg/kg (up to a maximum dose of 600 mg). Subjects ≥ 13 years of age will receive a single dose of 600 mg IV peramivir administered as a short IV infusion over a minimum of 15 minutes. Peramivir must be diluted in normal saline normal saline United States Pharmacopeia (SUP).:

Because of the risk of vasovagal reactions, particularly in children with needle phobia, it is recommended that subjects be in a supine position during peramivir administration. Appropriate post infusion observation should be performed.

9.2.2. Oseltamivir

Oseltamivir will be provided by the site's pharmacy as capsules or powder for oral suspension and prepared and used according to the manufacturer's instructions. Subjects will be dosed according to Table 2 below:

Table 2: Oseltamivir dose regimen by age

Age	Dose regimen				
≥ 13 years	75 mg BID for 5 days. Dose may be given as capsules or an oral suspension may be used by patients who cannot swallow a capsule.				
7-12 years	Weight based dosing:				
	\leq 15 kg 30 mg BID for 5 days				
	15.1 – 23 kg 45 mg BID for 5 days				
	23.1 – 40 kg 60 mg BID for 5 days				
	> 40 kg 75 mg BID for 5 days				
	Dose may be given as capsules or an oral suspension may be used by subjects who cannot swallow a capsule.				

9.3. Randomization and Blinding/ Masking

Subjects ≥ 7 to 17 years of age will be randomized to 1 of 2 treatment arms, at a ratio of 4:1:

Treatment Group 1: A single dose of IV peramivir

Treatment Group 2: Oral oseltamivir given BID for 5 days

Following approval of amendment 3, all subjects < 7 years old will receive a single dose of intravenous peramivir.

As this is an open label study, blinding is not applicable.

9.4. Study Medication Preparation and Administration

9.4.1. Peramivir

The Principal Investigator at each study center will designate a pharmacist (or other qualified study staff member) to prepare IV peramivir as described in a separate study Pharmacy Manual.

Prior to infusion, an appropriate amount of the peramivir 10 mg/mL stock solution will be diluted in saline using aseptic techniques with a maximum volume of 100 mL. Once prepared, solutions of peramivir in saline should be refrigerated and infused within 24 hours of preparation.

In children ≥ 12 months, the total peramivir dose should be diluted to a total volume of 100 mL. For children ≤ 12 months, the following dilution should be followed:

Table 3: Peramivir Dilution for Children < 12 Months of Age

Age		Dosing			
		Anticipated Approximate Volume of Undiluted Drug Product	Volume of Diluted Drug Product Infused	Total mEq of Na Infused	Number of Vials Per Dose
0 - < 28 days (3 kg to 5.5 kg)	Dilute dose to 12 mL total	2.4 to 4.4 mL	12 mL	1.5 to 1.2	1
28 days to < 3 months (3 kg to 7.5 kg)	Dilute dose to 20 mL total	2.4 to 6.0 mL	20 mL	2.7 to 2.2	1
3 months to < 6 months (4.5 kg to 11.2 kg)	Dilute dose to 25 mL total	3.6 to 4.7 mL	25 mL	3.3 to 3.1	1
6 months to < 12 months (4.5 kg to 11.2 kg)	Dilute dose to 25 mL total	7.2 to 13.4 mL	25 mL	2.7 to 1.8	1

The study drug should be given as soon as possible after enrollment and randomization on Day 1. The calendar date and 24-hour clock time (start and end of the IV infusion) will be recorded. If the intravenous line used to administer peramivir is also to be used to administer any other medications, it should be flushed with at least 5 mL of saline before and after peramivir administration. Peramivir should not be piggy-backed to any other medication being administered.

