- 5. Females who are pregnant (positive urine or serum pregnancy test) or breast-feeding at screening.
- 6. Onset of symptoms more than 72 hours before presentation for screening for subjects <2 years old.
- 7. Development of symptoms while hospitalized for another indication
- 8. Subjects with identified risk factors for influenza complications but with uncomplicated influenza at the time of enrollment are not excluded. This includes lung disease, heart disease, blood disorders such as sickle cell anemia, metabolic disorders and neurologic disease. In addition, mild to moderate immunocompromised status such as due to renal disease, diabetes mellitus or HIV infection with a last known CD4+ count ≥200 cells/µl are not excluded.
- 9. Presence of severe immunocompromised status due to chronic disease or illness, previous organ transplant, or use of immunosuppressive medical therapy which would include oral or systemic treatment with > 10 mg prednisone or equivalent on a daily basis within 30 days of screening.
- 10. Complicated influenza characterized by any of the following:
 - a. ICU care
 - b. Evidence of organ dysfunction
 - c. Proven or suspected concomitant bacterial infection
 - d. Other known concomitant viral infection that is likely to complicate medical course such as RSV, parainfluenza virus and adenovirus. Co-infection with rhinovirus and enterovirus is allowed.
- 11. Previous participation in Study BCX1812-305 or participation in a study of any investigational drug or device within the last 30 days.
- 12. Subjects who cannot comply with all aspects of the study protocol.

Investigational product, dosage and mode of administration:

Subjects assigned to receive peramivir, will receive an age-appropriate single dose of peramivir, diluted appropriately in normal saline, administered as a short intravenous infusion over a minimum of 15 minutes.

- Subjects ≥ 13 years will receive a dose of 600 mg.
- Subjects ≥ 6 months to ≤ 12 years will receive a dose of 12mg/kg (to a maximum dose of 600 mg).
- Subjects < 6 months will receive a dose of 8mg/kg.

Reference therapy, dosage and mode of administration:

Subjects randomized to oral oseltamivir will receive an age appropriate dose twice daily for 5 days.

- Subjects ≥ 13 years will receive a 75mg dose administered as a capsule or oral suspension (twice daily for 5 days).

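### Protocol Table 3: in the two infant rows either side of 6 months, one volume limit each does not fit the printed weights (4.7 mL should be 9.0 mL; 7.2 mL should be 5.4 mL)

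*Protocol*

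**What the plan says.** Three statements fix the volume of drug to draw.

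- Dose below 6 months (Protocol 9.2.1): "Subjects < 6 months of age at time of consent will receive a single dose of IV peramivir at a dose of 8 mg/kg". Section 9.1 gives the modelling basis for the split: "8 mg/kg from birth to less than 6 months of age, and 12 mg/kg in subjects 6 months of age and older".
- Dose from 6 months (Synopsis): "Subjects ≥ 6 months to ≤ 12 years will receive a dose of 12mg/kg". The 600 mg cap is not reached at infant weights.
- Stock (9.4.1): "an appropriate amount of the peramivir 10 mg/mL stock solution will be diluted in saline".

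For infants, 9.4.1 then says "the following dilution should be followed" and gives Table 3. Its two oldest rows are "3 months to < 6 months (4.5 kg to 11.2 kg" and "6 months to < 12 months (4.5 kg to 11.2 kg", with undiluted volumes of 3.6 to 4.7 mL and 7.2 to 13.4 mL. Both doses are made up to 25 mL from one vial. The sodium limits are 3.3 to 3.1 mEq and 2.7 to 1.8 mEq. The next younger row is "28 days to < 3 months (3 kg to 7.5 kg", with 2.4 to 6.0 mL. The volume column is labelled as anticipated and approximate, and 9.4.1 refers to a separate Pharmacy Manual for preparation.

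**The concern.** The two rows share one weight range but follow different dose rules, so their volume ranges should differ by a factor of 12/8 at both ends. They do not: 7.2/3.6 is 2.0 and 13.4/4.7 is 2.9.

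Within these documents, Table 3 is the only place where the infant mg/kg dose appears as a volume. Its practical use is as a check that a calculated draw is plausible for the child's age and weight. If a printed limit is wrong, a correct draw looks like an error, and someone may correct it in the wrong direction. The dose split at 6 months was chosen so that exposure in the youngest infants would be similar to that in adults, and these two rows sit on either side of that boundary.

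**Working it through.** **Formula.** Volume (mL) = weight (kg) × dose (mg/kg) ÷ 10 mg/mL. Weights, printed volumes, total volumes and sodium come from Table 3; doses and stock come from the sections cited above. The last column is printed sodium ÷ (total volume − printed drug volume), in mEq/mL. Total volumes are 12, 20, 25 and 25 mL.

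| Row | Weight (kg) | mg/kg | Computed mL | Printed mL | Na ÷ saline volume |
|---|---|---|---|---|---|
| 0 to < 28 days | 3 | 8 | 2.4 | 2.4 | 0.156 |
| 0 to < 28 days | 5.5 | 8 | 4.4 | 4.4 | 0.158 |
| 28 days to < 3 months | 3 | 8 | 2.4 | 2.4 | 0.153 |
| 28 days to < 3 months | 7.5 | 8 | 6.0 | 6.0 | 0.157 |
| 3 to < 6 months | 4.5 | 8 | 3.6 | 3.6 | 0.154 |
| 3 to < 6 months | 11.2 | 8 | **8.96** | **4.7** | 0.153 |
| 6 to < 12 months | 4.5 | 12 | **5.4** | **7.2** | 0.152 |
| 6 to < 12 months | 11.2 | 12 | 13.44 | 13.4 | 0.155 |

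**Six limits reproduce** to rounding, so the formula is the one the table was built on.

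**Two do not.**
- 4.7/8.96 = 0.52, or 48% low. Read against 11.2 kg, 47 mg is 4.2 mg/kg.
- 7.2/5.4 = 1.33, or 33% high. Read against 4.5 kg, 72 mg is 16 mg/kg.

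**Weights that the two volumes would fit.** 47 mg ÷ 8 mg/kg = 5.875 kg, and 72 mg ÷ 12 mg/kg = 6.0 kg. A correct draw therefore leaves the printed range above about 5.9 kg in the first row and below 6.0 kg in the second. One explanation is that a single 3 to < 12 months row was split near 6 kg and its weight label kept in both halves. That is inference.

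**Are 4.7 and 7.2 misreads of the PDF?** Unlikely. As printed, all eight limits give 0.152 to 0.158 mEq of sodium per mL of saline. With the weight-based volumes and the printed sodium, the two limits would give 3.1/(25 − 8.96) = 0.193 and 2.7/(25 − 5.4) = 0.138. The printed sodium was computed from 4.7 and 7.2 mL.

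**Sodium after correction.** Assume saline at 0.154 mEq/mL. The documents do not state this value, but it reproduces all eight printed sodium figures to one decimal from the printed volumes. Then (25 − 8.96) × 0.154 = 2.5 mEq and (25 − 5.4) × 0.154 = 3.0 mEq.

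**Cells that still hold.** 8.96 mL and 5.4 mL both fit within the 25 mL total and within one 20 mL vial.

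**The case against.** The strongest reply is that Table 3 does not set the dose. The mg/kg rule does, and each row takes the dose as given and states the volume to make it up to. The instruction to follow the table concerns dilution. The disputed column is a range per age row, labelled approximate, and nobody can read one child's volume from it. Staff may work from the Pharmacy Manual and never see it.

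Most of this stands, and it rules out a stronger reading. A reader might infer that the table directs infants to 4.2 or 16 mg/kg, or that infants were misdosed. The documents do not support that. Those figures come from pairing a printed volume with the weight at the same end of its row; nothing in the protocol prescribes them or tells anyone to cap or floor a draw at the printed limits. Only if someone did so would a dose change: a 7.5 kg infant of 3 to < 6 months should get 60 mg (6.0 mL), and a draw cut to 4.7 mL would give 47 mg, which is 6.3 mg/kg or 22% low.

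Two parts do not stand. Approximation does not cover gaps of −48% and +33% when the other six limits agree to rounding. Nor can the volumes be saved by treating only the weight labels as wrong or misread, a possibility the sodium check does not test. That would cap the 3 to < 6 months row at about 5.9 kg, while the younger row, at the same 8 mg/kg, runs to 7.5 kg and 6.0 mL.

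**Conclusion.** The point holds as a minor internal inconsistency in an operative preparation table. Two of eight volume limits, and the two sodium limits computed from them, contradict the weights in their own rows under the protocol's dose rule and stock strength. The consequence is that the table fails as a check for heavier infants of 3 to < 6 months and lighter infants of 6 to < 12 months, where a correct draw may be queried or wrongly adjusted.

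The conclusion on volumes rests only on figures printed in the protocol; the corrected sodium figures also rest on the 0.154 mEq/mL assumption. Which element was mistyped, weight or volume, is not known, and the inconsistency exists either way. How many infants fall outside the printed ranges cannot be derived, because the documents give no weight distribution. Whether the Pharmacy Manual repeats the table cannot be seen from here. Nothing in the design, dosing rule or analysis changes.

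**What to change.** Choose one of two corrections.

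1. If the printed weights are intended, reprint 3 to < 6 months as 3.6 to 9.0 mL with 3.3 to 2.5 mEq Na, and 6 to < 12 months as 5.4 to 13.4 mL with 3.0 to 1.8 mEq Na (saline at 0.154 mEq/mL).
2. If different weights were intended, print the range for each row and recompute volume and sodium from it. Check that the 3 to < 6 months row remains plausible beside the younger row's 7.5 kg.

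In either case, add the mg/kg dose to each row so that the volumes can be verified at sight, and check the Pharmacy Manual for the same table. The cost is two volume and two sodium limits under the first option, or two weight labels and the dependent figures under the second.

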9.4.2. Oseltamivir

Oseltamivir will be prepared and administered in accordance with the manufacturer's instructions.

9.5. Treatment Compliance

Intravenous peramivir will be administered by study staff or other qualified personnel. Details of the infusion (to include date of dose, start time, and stop time) will be recorded by a member of the study staff.

The first dose of oral oseltamivir will be administered in capsule or oral solution form at the site by study staff or other qualified personnel. Details of the first and all subsequent doses (administered at home by the subject/parent/guardian) will be recorded in the Subject Diary. Details will include the date and time of drug administration.

9.6. Overdose and Toxicity Management

To date there is no experience with overdose of IV peramivir. If overdose occurs, subjects should receive indicated supportive therapy and evaluation of hematologic and clinical chemistry

laboratory tests should be conducted. Peramivir is cleared by hemodialysis; the decision to use hemodialysis should be addressed on a case-by-case basis with the Sponsor.

9.7. Study medication accountability

The Investigator/pharmacist must maintain accurate records of the disposition of all study drug received from the Sponsor and administered to the subject (including date and time), and any drug accidentally destroyed. The Sponsor will supply a specific Drug Accountability Form. At the end of the study, information describing study drug supplies (e.g., lot numbers) and disposition of supplies for each subject must be provided, signed by the Investigator or designee, and collected by the Study Monitor. If any errors or irregularities in any shipment of study medication to the site are discovered at any time, the Sponsor Project Manager must be contacted immediately.

At the end of the study, all medication that was neither dispensed or administered, as well as packaging materials will be collected with supervision of the monitor and returned to the Sponsor or destroyed on site as dictated by the appropriate Standard Operating Procedure (SOP) at the participating site

9.8. Concomitant Medications

Administration of a concomitant medication during the study period must be recorded within the subject's medical records. This includes prescription medications as well as over-the-counter medications.

Medications used for the symptomatic treatment of influenza-related symptoms will be discouraged for children 2-5 years of age as per American Academy of Pediatrics guidance and the January 2008 FDA public health advisory. Parents/caregivers will be requested to follow package labeling for over-the-counter cold and influenza symptom relief medications for children 2-5. The use of symptomatic medication will be prohibited in children < 2 years of age. Antipyretics will be permitted in all age groups. Parents/caregivers will record the date, time, and dose of symptomatic medications and antipyretics in the Subject Diary. All other concomitant medications will be transcribed from the source onto the Case Report Form (CRF) by study staff.

Use of concomitant medications will be assessed and recorded at Screening/ Baseline, and daily throughout the duration of the study through the study follow-up visit.

9.8.1. Medications for Chronic Diseases/Conditions

Subjects with chronic medical conditions may continue to receive prescribed treatments during participation in this protocol. The exception is high dose steroids > 10 mg/day (see exclusion criteria, Section 8.2).

9.8.2. Antivirals

There are no known adverse interactions of peramivir with other influenza antivirals (such as oseltamivir, zanamivir, amantadine, and rimantadine); however, their concomitant use is not permitted during administration of study drug and in the post-treatment follow-up period.

9.8.3. Corticosteroids

Corticosteroids at dose < 10 mg a day are allowed during administration of the study drug and throughout study participation.

9.8.4. Antipyretics and Analgesics

Resolution of fever is a major component of some of the clinical effectiveness endpoints for this study. Accordingly, use of any antipyretics or analgesics with antipyretic properties must be carefully controlled and documented. Antipyretics and analgesics may be administered while the subject is enrolled in this study. The names and dosages of these medications will be recorded in the Subject Diary. To avoid the confounding effects of antipyretic medications, temperature measurements, including those recorded by study staff while in the emergency department or clinic and those recorded by the subjects during the follow-up period, will be taken, whenever possible, at least 4 hours after administration of the antipyretic medication or immediately prior to administration. Following discharge from the hospital, the names and dosages of all other medications will be recorded in the Subject Diary by the parent/ care-giver.

Temperature measurements that are recorded for the purpose of analyzing effectiveness in this study < 4 hours after administration of the antipyretic medication, regardless of the dose, will not be counted in the effectiveness analyses.

9.8.5. Antibiotics

Oral or parenteral antibiotics may be administered, if medically indicated. If such use is a result of proven or suspected influenza-related complication, appropriate assessments should be carried out (see Section 11.4).

10. STUDY CONDUCT

10.1. Overview

Up to 140 subjects will be enrolled in this study according to the following age groups:

- Birth to < 28 days: up to 10 subjects, given IV peramivir
- 28 days to < 2 years: up to 20 subjects: subjects enrolled after the approval of amendment 3 will receive IV peramivir
- 2 < 4 years: up to 10 subjects: subjects enrolled after the approval of amendment 3 will receive IV peramivir
- 4 < 7 years:up to 30 subjects: subjects enrolled after the approval of amendment 3 will receive IV peramivir
- 7 < 13 years:up to 40 subjects, randomized 4:1 to IV peramivir or oral oseltamivir
- 13 < 18 years:up to 30 subjects, randomized 4:1 to IV peramivir or oral oseltamivir

Once an age cohort is filled, enrollment in that cohort will be closed and communicated with all investigators.

A subject's duration of participation in this study is expected to be 14 days.

Subjects meeting the inclusion/exclusion criteria may be enrolled into the study. It is expected that most subjects will have the Screening/Baseline Visit and the Day 1 Treatment Visit on the same day.

All subjects will receive either a single dose of IV peramivir (600 mg, or12 mg/kg or 8 mg/kg or depending on age) or oral oseltamivir, dosed BID for 5 days. *Note, as of the approval of amendment 3, no additional subjects will be randomized to receive oseltamivir.*

Subjects will undergo follow-up assessments on Days 3, 7, and 14. The Day 3 visit may be a home visit (performed by a qualified study nurse). Day 7 is required to take place in the clinic, and Day 14 may either be a clinic visit, home visit, or follow-up phone call to the subject/parent/guardian.

All parents/caregivers will record the following information in the Subject Diary.

- Temperature measurements (oral or axillary) will be taken with an electronic thermometer provided by BioCryst, approximately every 12 hours until temperature normalizes for 48 hours (i.e., temperature without antipyretic is < 99.4 orally in children ≥ 6 and < 98.4 axillary in children < 6 years old for 4 measurements). With the exception of the baseline measurement, all temperature measurements will be obtained at least 4 hours after, or immediately before, administration of oral acetaminophen or other antipyretic medications, if taken.
- Date and time of oral oseltamivir dose administration, if applicable. This should be recorded in the Subject Diary twice a day for 5 days.
- Doses of antipyretic medication and any medications taken for symptomatic relief, each day through the last follow-up assessment.

- The ability of the child or adolescent to return to day care/school and/or resume their normal "pre-illness" daily activity will be assessed once daily until the child or adolescent returns to day care/school and/or resume normal "pre-illness" daily activity.
- The child or adolescent's appetite and eating patterns assessed as normal or reduced/abnormal will be assessed once daily until they return to normal "pre-illness" level.

All parents/caregivers of subjects 7 years of age and older will record the following additional information in the Subject Diary:

• Assessment of 7 influenza symptoms (cough, sore throat, nasal obstruction, myalgia [muscle aches), headache, feverishness, and fatigue) on a 4-point severity scale (0, absent; 1, mild; 2, moderate; 3, severe) twice daily, beginning pre-dose on Day 1 until symptom resolution or through the last follow-up visit, (whichever comes first).

All parents/caregivers of subjects ≥ 4 years of age to ≤ 6 years of age will record the following additional information in the Subject Diary:

• Assessment of 7 influenza symptoms [cough, sore throat, nasal obstruction, myalgia (muscle aches), headache, feverishness, fatigue/malaise, and gastrointestinal symptoms (nausea, vomiting or diarrhea)] on a 4-point severity scale (0, absent; 1, mild; 2, moderate; 3, severe) twice daily, beginning pre-dose on Day 1 until symptom resolution or through the last follow-up visit, whichever comes first.

All parents/caregivers of subjects \le 3 years of age will record the following additional information in the Subject Diary:

• Assessment of 5 influenza symptoms [cough, rhinitis, feverishness, malaise/irritability and gastrointestinal symptoms (nausea, vomiting or diarrhea)] on a 4-point severity scale (0, absent; 1, mild; 2, moderate; 3, severe) twice daily, beginning pre-dose on Day 1 until symptom resolution or through the last follow-up visit, (whichever comes first).

An adequate nasal swab specimen will be collected from all enrolled subjects at Baseline (pre-dose) for virus sub-type identification and quantitative virologic assessments and at the follow-up assessments on study Days 3, 7, and where possible Day 14.

Specimens from all subjects yielding influenza virus will also be assessed for susceptibility to neuraminidase inhibitors (Day 1 and last specimen yielding influenza virus on culture). A central laboratory will perform all virologic assessments.

Plasma samples for determination of drug concentration on subjects randomized to peramivir will be drawn as follows:

Up to 4 blood samples will be drawn, where possible, during the following time periods, beginning from the end of dosing until release from the site

- One time point immediately following completion of the infusion
- One time point from 30 minutes to 1 hour post-infusion

- One time point from 1 hour to 3 hours post-infusion
- One time point from 3 hours to 6 hours post-infusion

Note: Subjects \geq 5 kg will have four 1.0 mL PK blood draws at the above stated sampling times. Subjects \leq 5 kg will have two 1.0 mL blood samples; one time immediately following completion of the infusion and one time between 1-3 hours post-infusion.

Adverse events and concomitant medications will be monitored at each scheduled visit from the screening/baseline assessment to final study visit. Clinical laboratory investigations (chemistries, hematology, and urinalysis) will be collected at baseline and at the final study visit. Safety and tolerability will be evaluated through assessments of adverse events, laboratory analyses (clinical chemistry, hematology, and urinalysis), vital signs and physical examinations at the time points indicated in the schedule of assessments.

